4.2 Biopsies

At baseline, if patient does not have frozen tissue available (see section 6.6) fresh tissue must be obtained. If possible, the pre-treatment biopsy should be performed after all other eligibility criteria are confirmed. Enough tissue will be collected for both kinomining and NextGen sequencing if available (see section 6.6). Fresh tissue collection of accessible tumor will be repeated **at progression (clinical or radiological)** whether patient continues treatment post progression or

not. In fact, patients will be requested to remain on study medication until the biopsy at progression is performed. For subjects who are withdrawn from study treatment, but are later placed back on the trametinib/dabrafenib combination therapy, a biopsy may be collected from the former study subject at the time of progression from the standard of care trametinib/dabrafenib therapy. These subjects must be consented and placed back on study to allow for attainment of a biopsy at progression. These subjects will then remain on study for safety monitoring, in relation to the biopsy procedure, for 30 days. Subjects who have an ongoing \geq grade 2 or serious AE (SAE) related to the study procedure at 30 days will continue to be followed until the event is resolved or deemed irreversible by the investigator.

If possible, biopsies at progression should be performed within 7 business days of documented disease progression, and optimally within 4 hours of taking that day's study medication. If treating physician decides to continue treatment because the patient exhibits continued clinical benefit from therapy (and the patient agrees) then the biopsy can be delayed until the investigator deems the biopsy feasible as long as patient safety is not compromised. Post-treatment biopsies will not be required for patients removed for reasons other than disease progression; although, as mentioned above, if these subjects then go on to eventually receive the trametinib/dabrafenib combination in the future, as part of their standard of care, of the subject may be re-consented at the time of disease progression. See section 6.6 and laboratory manual. Please also see the note in section 6.9.3 regarding assessment of biopsied lesions per RECIST v1.1.

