3.2.16 Pregnant or lactating female

3.3 Inclusion Criteria for Off-Study Subjects to Receive Progression Biopsy

3.3.1 Currently progressing on Trametinib/Dabrafenib Combination Therapy

3.3.2 Willing to undergo biopsy for research purposes only.

[figure not shown]
3.3.3 Tumor amenable to research biopsy.

3.3.4 Signed written informed consent to have a progression biopsy performed on the LCCC 1128 protocol.

3.3.5 Previously enrolled on the LCCC 1128 study and did not have a progression biopsy previously performed while on study.

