6.5 End of Treatment

This visit should occur in patients when they permanently stop treatment for any reason, and should be performed 30 days (+/-7 days) after the last dose of study medication.

Clinical evaluation: complete history, physical examination (to also include vital signs and weight), and ECOG performance status.

Laboratory studies:

- **Hematology**: Hematology includes the following parameters: CBC with differential, Hgb, and platelet count.
- **Serum Chemistries**: These include the following parameters: creatinine, sodium, potassium, calcium, magnesium, phosphorus, albumin, total bilirubin, AST (SGOT) and ALT (SGPT).

Concomitant medications: Review any additions or deletions

Patient Diary: Review Diary

Toxicity Assessment: Using NCI CTCAEv4; Patients who have an ongoing grade 4 or serious AE (SAE) at the time of discontinuation from treatment will continue to be followed until the event is resolved or deemed irreversible by the investigator, and will then be followed-up per protocol. Toxicity assessment should include interrogation of the patient related to any visual changes they may be experiencing.

Tissue acquisition: Biopsy of accessible tumor will be done in patients who stop treatment due to progression, if possible within 7 business days of documented disease progression, and optimally within 4 hours of taking that day's study medication. Post-treatment biopsies will not be required for patients removed for reasons other than disease progression. See section 6.7 and laboratory manual.

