6.7 Correlative Study Procedures

For both those patients who do and do not co-enroll into LCCC1108, we will ask for a blood sample (~8mLs in a yellow-top ACD tube) to ensure sufficient germline DNA in the event tissue samples are insufficient. This request and collection may take place at any point during the study, including during follow-up.

At baseline, if patient does not have frozen tissue available, fresh tissue must be obtained by biopsy. Biopsy of tumor will be repeated at or after progression (clinical or radiological) whether patient continues treatment post progression or not. If possible, biopsies at progression should be performed within 7 business days of documented disease progression, and optimally within 4 hours of taking that day's study medication. Please note that drug may be extended post progression (see section 4.1), and there is no need to hold drug for any length of time prior to the biopsy. In fact, patients will be requested to remain on study medication until the biopsy at progression is performed. If the treating physician decides to continue treatment at progression because the patient exhibits continued clinical benefit from therapy, the biopsy may be delayed until the investigator deems the biopsy feasible as long as patient safety is not compromised. Post-treatment biopsies will not be required for patients removed for reasons other than disease progression. See laboratory manual.

Note: For subjects who are withdrawn from study treatment, but are later placed back on the trametinib/dabrafenib combination therapy, a biopsy may be collected from the former study subject at the time of progression from the standard of care trametinib/dabrafenib therapy. These subjects must be re-consented and placed back on study to allow for attainment of a biopsy at progression.

Biopsies may be obtained by punch biopsy, core biopsy, or surgical excision, and may be performed by clinical personnel trained to do biopsies for standard of care collections. The number of - passes made through tumor per biopsy will be determined by the treating physician and the physician performing the biopsy procedure with primary consideration being safety. The tissue collected will be divided into aliquots (depending on size of collection, up to 4 aliquots per collection). For patients who co-enroll into LCCC1108 for NextGen sequencing, enough tissue will be collected for both kinomining and NextGen sequencing by

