6.9 Assessment of Primary Endpoint and Efficacy

Provided sufficient tumor tissue is available pre and post treatment (specifically at progression) to perform kinomining, data from the patient will be utilized to inform the primary objective. If a patient drops out of the study prior to progression, they may be replaced. See section 4.9 for additional information. For subjects who are withdrawn from study treatment, but are later placed back on the trametinib/dabrafenib combination therapy, a biopsy may be collected from the former study subject at the time of progression from the standard of care trametinib/dabrafenib therapy. Information from these biopsies will be included in the analysis of the primary objective and the correlative secondary objective.

Patients who have received at least 2 cycles of therapy and have their disease re-evaluated after 2 cycles will be evaluable for assessment of objective response. Patients who drop out of the study prior to this point will not be evaluable for response unless their disease progressed prior to this point.

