6.9.3 Evaluation of Target Lesions using RECIST 1.1 Criteria

NOTE: Whenever possible, a biopsied lesion should not be considered a target lesion for RECIST tumor assessments. If the biopsied lesion is the only site of measurable disease, it may only be followed as a target lesion if a core biopsy was performed. Lesions that have been completely removed or subjected to excisional biopsy should not be followed as target lesions.

NOTE: In addition to the information below, also see section 4.3.2 in the international criteria proposed by the Response Evaluation Criteria in Solid Tumors (RECIST) Committee, version 1.1 (Eur J Cancer 45;2009:228-247) for special notes on the assessment of target lesions.

Complete response (CR)—Disappearance of all target lesions. Any pathological lymph node (LN) target or no must have decreased in short axis to <10mm.

Partial response (PR)—At least a 30% decrease in the sum of the LD of the target lesions taking as reference the baseline sum LD.

Progressive Disease (PD)—At least a 20% increase in the sum of the LD of the target lesions taking as reference the smallest sum LD recorded since the treatment started including baseline if that is the smallest on study. In addition to the relative increase of 20%, the sum must also demonstrate an absolute increase of at least 5mm. The appearance of one or more new lesions also constitutes PD.

Stable disease (SD)—Neither sufficient shrinkage to qualify for PR nor sufficient increase to qualify for PD taking as references the smallest sum LD since the treatment started.

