8.0 STATISTICAL CONSIDERATIONS

8.1 Sample Size and Data Analysis Plans

Our sample size justification is based on the primary objective to identify kinases which are differentially expressed between pre (just prior to treatment initiation) and post treatment (patients who developed resistance) after treatment with BRAF+MEK inhibition in melanoma patients.

The kinases will be profiled using Multiplexed Inhibitor Beads (MIBs) coupled with mass spectrometry. We anticipate this technique to capture between 50 – 100 kinases in melanoma patients. The kinase activity is reported as a quant ratio between the experimental and control samples. The Paragon algorithm[10] automatically identifies high confidence peptides that will contribute to the average quant ratio of a kinase. Our sample size justification is based on our ability to detect a meaningful difference in the kinase activity between pre and post treatment. The inherent matching of tumor by patient source pre and post treatment will provide a potential source of positive correlation that may be exploited to improve statistical power (e.g., using a paired t-test). However, in order to be conservative, we compute our statistical power using a two-tailed independent Mann-Whitney test in which the kinase activity is compared in the two groups. Based on preliminary data, we assume that 100 kinases are captured, of which 10% of them are truly differentially expressed between pre and post treatment and a common standard deviation of 0.95 (in \log_2 scale).

Table 1 summarizes the power to detect a true difference of D with a sample size of 20 tumors in each group (pre and post treatment) at FDR of 0.05 to account for multiple testings. For example, we achieve a power of 0.92 to detect a \log_2 difference of 1.32 (or a fold change of 2.5) for each kinase between pre and post treatment.

D=Difference in \log_2 scale	1.00	1.32	1.58	1.81
Fold change (2^D)	2	2.5	3	3.5
Power	0.59	0.92	0.99	1.00

Data Analysis Plans

Exploratory tools such as heatmaps and two-way unsupervised hierarchical clustering will be utilized as visual representation of overall kinome activity. The

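### The plan lets the progression biopsy come from any accessible lesion, so tissue from a non-progressing lesion can be analysed as resistant and no required record would show it

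*Combined protocol and SAP*

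**What the plan says.** Five places set the progression biopsy. None conditions on the state of the lesion sampled.

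- Section 4.2, repeated in footnote 13 of the Time and Events Table (Section 6.1): "Fresh tissue collection of accessible tumor will be repeated" at progression.
- Section 6.5: "Biopsy of accessible tumor will be done in patients who stop treatment due to progression". Progression here describes the patient.
- Section 6.7: "Biopsy of tumor will be repeated at or after progression (clinical or radiological", with no site named.
- Section 3.3.3, for former subjects who return for a biopsy: "Tumor amenable to research biopsy".

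If treatment continues past progression because of clinical benefit, Section 4.2 adds that "the biopsy can be delayed until the investigator deems the biopsy feasible as long as patient safety is not compromised".

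Progression is a patient-level call. It may be clinical or radiological, and under Section 6.9.3 "The appearance of one or more new lesions also constitutes PD". Section 6.9 governs entry to the primary analysis: "Provided sufficient tumor tissue is available pre and post treatment (specifically at progression) to perform kinomining, data from the patient will be utilized". Section 8.1 describes the second group as "post treatment (patients who developed resistance".

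**The concern.** The resistance label belongs to the patient, but the assay is run on a piece of one lesion. A patient can progress through one new lung or brain lesion while skin or nodal disease is still responding. The skin lesion is the accessible one. A site that biopsies it follows every section above, and the sample goes into the post-treatment group as resistant.

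Two things would be at stake. First, such a sample dilutes the pre/post difference for kinases that mark resistance. Second, a responding lesion on drug need not look like baseline. Section 1.6.1 reports kinome reprogramming under MEK inhibition in breast cancer models, and Section 1.3.1 reports a median 62% inhibition of pERK in melanoma biopsies on trametinib 2 mg. Differences of that kind are real drug effects, so FDR control would not remove them, yet they would be read as resistance. The PAM signature and the mutation comparison in Section 8.1 use the same label.

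The problem could not be seen afterwards from the data the protocol requires. No section asks for the identity or status of the sampled lesion. Section 6.9.3 prefers that biopsied lesions not be target lesions, and Section 6.9.2 does not require non-target lesions to be measured.

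**Working it through.** **Inputs from Section 8.1.** 20 tumors per group; two-sided Mann-Whitney, unpaired; FDR f = 0.05; 100 kinases, of which m1 = 10 truly differ and m0 = 90 do not; SD 0.95 on the log2 scale. Stated power is 0.59, 0.92, 0.99 and 1.00 at log2 differences D of 1.00, 1.32, 1.58 and 1.81.

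**Assumed, not in the documents.** The share c of post-treatment samples from non-progressing lesions, taken as 2 of 20 (0.10) or 4 of 20 (0.20), and the part of the resistance shift that those samples carry (none, or half).

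**Step 1: reproduce the plan's figure.** The per-kinase alpha implied by the FDR is alpha = m1 × power × f / (m0 × (1 − f)), solved jointly with power. Power comes from a two-sided noncentral t with 38 df and noncentrality D / (SD × √(2/20)).

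At D = 1.32 the noncentrality is 1.32 / 0.3004 = 4.39, alpha = 10 × 0.917 × 0.05 / (90 × 0.95) = 0.0054, and power is 0.917. The four columns come out at 0.585, 0.917, 0.987 and 0.998, so the table reproduces. A simulated Mann-Whitney test with Benjamini-Hochberg gives slightly less: 0.87 at D = 1.32.

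**Step 2: affected samples carry none of the shift.** The mean difference becomes D(1 − c), and the post-group variance becomes SD² + c(1 − c)D².

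- c = 0.10: mean 1.188 (fold change 2.28 instead of 2.5); variance 0.9025 + 0.09 × 1.7424 = 1.059; SE √((0.9025 + 1.059)/20) = 0.313; noncentrality 3.79; power 0.77.
- c = 0.20: mean 1.056 (fold change 2.08); variance 0.9025 + 0.16 × 1.7424 = 1.181; SE 0.323; noncentrality 3.27; power 0.56.

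**Step 3: affected samples carry half the shift.** The mean is D(1 − c/2) and the variance is SD² + c(1 − c)(D/2)².

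- c = 0.10: mean 1.254, SE 0.304, noncentrality 4.13, power 0.87.
- c = 0.20: mean 1.188, SE 0.306, noncentrality 3.88, power 0.80.

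**Step 4: leave the affected pairs out instead.** With the Step 1 formula at 18 per group, power is 0.87; at 16 per group it is 0.80.

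Results at D = 1.32:

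| | 0 of 20 | 2 of 20 | 4 of 20 |
|---|---|---|---|
| No shift, noncentral t | 0.92 | 0.77 | 0.56 |
| No shift, simulated Mann-Whitney | 0.87 | 0.72 | 0.46 |
| Half shift, noncentral t | 0.92 | 0.87 | 0.80 |
| Half shift, simulated Mann-Whitney | 0.87 | 0.82 | 0.74 |
| Affected pairs left out, noncentral t | 0.92 | 0.87 | 0.80 |

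On the noncentral t scale, leaving affected pairs out gains power if they carry no shift and is neutral at half shift. In the second case the reason to separate them is the label, not power.

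The loss depends on D. With no shift in the affected samples, power at D = 1.00 falls from 0.59 to 0.38 or 0.19; at D = 1.81 it is still 0.89 with 4 of 20.

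**The case against.** The strongest reply is that this is permitted, not shown. The documents give no rate of mixed response and no rate of sampling the wrong lesion, and both must happen in the same patient. Investigators may often choose a progressing lesion unprompted. That stands: 10% to 20% is an assumption, and a reader should not infer that responding tissue does enter the analysis.

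A reader might also infer that the trial would then fail to measure its primary objective. The documents do not support that. Section 2.3.1 defines the endpoint as a comparison of pre- and post-treatment biopsies, and the first half of Section 2.1 concerns kinases that differ before and after treatment, which any on-treatment sample informs. Only the resistance half, and the label in Section 8.1, depend on lesion status.

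Section 8.1 calls the unpaired test conservative and mentions a paired t-test. Simulated paired power at D = 1.32 with 0, 2 and 4 zero-shift samples is about 0.97, 0.9 and 0.7 at an assumed within-patient correlation of 0.3, and about 1.00, 0.98 and 0.89 at 0.5. With no correlation there is no relief (about 0.87, 0.7 and 0.44). The documents give no correlation, so pairing may help but cannot be counted on.

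Progressing lesions are also sampled on drug, since Sections 4.2 and 6.7 ask patients to stay on medication until the biopsy. Choosing a progressing lesion therefore does not remove drug-exposure effects in general. This stands too.

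Two smaller replies carry less weight. The laboratory manual was not available, but Section 6.7 describes its scope as processing, storage and handling, not lesion choice. The study is small and exploratory and leaves the biopsy to safety-led judgement; that argues for a preference with a fallback, not for silence about which lesion was taken.

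**Conclusion.** The gap is real. No section ties the progression sample to a progressing lesion, admission rests on sufficient tissue, and the resistance label is set by patient. Tissue from a non-progressing lesion can enter the resistance comparison, the PAM signature and the mutation comparison under that label, and nothing the protocol requires to be recorded would identify it.

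The size is conditional. With 2 or 4 of 20 samples affected and carrying none of the shift, power at D = 1.32 drops from 0.92 to about 0.77 or 0.56. With half the shift, or with useful pairing, the loss is smaller. False resistance findings from drug effect are plausible but have not been quantified. The point should be fixed because the remedy is cheap; it does not invalidate the design.

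**What to change.** 1. In Sections 3.3.3, 4.2, 6.5 and 6.7 and in footnote 13 of Section 6.1, add that the progression sample should come from a new or progressing lesion where one can be safely reached, and otherwise from another accessible lesion. This has to be an addition fitted to each text, because Sections 3.3.3 and 6.7 word the requirement differently from the other three.
2. Record for each progression sample the lesion identifier, the site, and the status at the assessment that documented progression: new, growing, stable, shrinking or not determinable.
3. In Sections 6.9 and 8.1, pre-specify that the resistance comparison and signature use samples from new or progressing lesions, and show the all-samples pre/post result alongside.

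No procedure is added. The costs are a few eCRF fields, a status that cannot be determined for some unmeasured non-target lesions, and a smaller resistance set: unpaired power of about 0.87 with 18 pairs or 0.80 with 16 at D = 1.32. If biopsies are already complete, lesion status can be sought from existing scans and biopsy records, and the analysis rule fixed before the kinome data are examined.

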4.3 Treatment Dosage and Administration

Drug	Dose, Route & Schedule	Cycle
Trametinib	2 mg orally once daily	Every 3 weeks
Dabrafenib	150mg orally twice daily	Every 3 weeks

- After the pre-treatment biopsy is complete, patients will begin 2.0 mg of trametinib orally once per day in combination with dabrafenib 150mg PO BID.
- Patients will be instructed to take their dabrafenib at approximately the same time each day. The evening dose of dabrafenib should be administered approximately 12 hours after the morning dose.
- Both drugs should be administered under fasting conditions, either one hour before or 2 hours after a meal, and with approximately eight ounces of water.
- If a subject vomits after taking study medication, the subject should be instructed not to retake the dose and should take the next scheduled dose.
- If a patient misses a dose of dabrafenib, it should not be taken if it is less than 6 hours until the next dose. If a dose of trametinib is missed, the dose should only be taken if it is more than 12 hours until the next scheduled dose.

- Any missed dose should be noted on the patient diary (provided as a document separate from the protocol-see Appendices, section 11.6, for a model diary).

Note: loperamide should be made available prior to start of study treatment to patient so loperamide administration can begin at the first signs of diarrhea (see section 4.4.6).

4.4 Dose Modifications for Trametinib and Dabrafenib for Toxicity

See sections 5.1.5, 5.2.5, and appendices (section 11.3), and the respective IBs for additional information on drug-related toxicities. Any patient who receives treatment on this protocol will be evaluable for toxicity. Each patient will be assessed every 3 weeks for the development of any toxicity according to the Time and Events table (see Section 6.0). Toxicity will be assessed according to the NCI CTCAE, v 4.

If a patient experiences ≥ 2 or more AEs simultaneously that require different dose reductions, the lower dose should be used. Unless otherwise noted in the following sections, a maximum of 2 dose-level reductions for AEs are allowed on this protocol. If >2 dose reductions are required, protocol therapy is to be discontinued and patient is to be followed per protocol.

With the exception of decreased LVEF, both therapies should be reduced simultaneously in response to toxicities that are considered by the investigator to be treatment related. Note that if dabrafenib is permanently discontinued, trametinib will also be permanently discontinued.

Unless otherwise noted in the tables below, if an AE resolves to grade 1 or baseline at the reduced dose level, and no additional toxicities are seen after 4 weeks of study treatment at the reduced dose, the dose may be increased to the previous dose level in consultation with the study PI if so noted in the tables.

For AEs that require dose reductions, please refer to the dose levels in the following tables.

Trametinib Dose Levels for Toxicity		
Dose Levels	Dose, Route and Schedule	Dosage Strength
0	2 mg PO QD	2.0 mg tablets
-1	1.5 mg PO QD	0.5mg tablets
-2	1 mg PO QD	0.5mg tablets

Dabrafenib Dose Levels for Toxicity		
Dose Levels	Dose, Route and Schedule	Dosage Strength
0	150 mg PO BID	75 mg capsules
-1	100 mg PO BID	50 mg capsules
-2	75 mg PO BID	75 mg capsules

A dose reduction below 75 mg BID for dabrafenib and 1 mg once daily for trametinib is not allowed. If a dose reduction below 75 mg BID for dabrafenib is required, trametinib will also be permanently discontinued. If a dose reduction below 1.0 mg once daily for trametinib is required, then trametinib will be permanently discontinued, but these subjects will be allowed to continue dabrafenib.

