4.4.3.3 Reduced Left Ventricular Ejection Fraction

Decreases of the left ventricular ejection fraction (LVEF) have been observed in subjects receiving trametinib monotherapy and in combination with dabrafenib. Therefore, ECHOs must be performed to assess cardiac ejection fraction at regular intervals. ECHOs should be performed at baseline and at follow-up visit(s) See Time and Events table (section 6.1 for timing of follow-up ECHOs. Dose modification guidance and stopping criteria for LVEF decrease are provided in the table below.

LVEF-drop (%) or CTCAE grade	Action and Dose Modification

Asymptomatic* Absolute decrease of $\geq 10\%$ in LVEF compared to baseline and ejection fraction below the institution's LLN
 
*NOTE: symptoms may include dyspnea, orthopnea, and other signs and symptoms of pulmonary congestion and edema
	
Interrupt study treatment (both drugs) and repeat ECHO within 2 weeks. If LVEF has not recovered in 2 weeks, repeat 2 weeks later.
 
If the LVEF recovers within 4 weeks (defined as LVEF \geqLLN and absolute decrease $\leq 10\%$ compared to baseline):
 
 • Restart with trametinib reduced by one dose level in consultation with study PI • Restart dabrafenib at previous dose level • Repeat ECHO 2, 4, 8 and 12 weeks after re-start; continue in intervals of 12 weeks thereafter 
If LVEF does not recover within 4 weeks
 
 • Consult with cardiologist • Permanently discontinue trametinib • Report as SAE • Repeat ECHO after 2, 4, 8, 12, and 16 weeks or until resolution • Consult with study PI regarding restart of dabrafenib once LVEF recovers

Symptomatic* Grade 3: resting LVEF 39-20% or $>20\%$ absolute reduction from baseline
	
Permanently discontinue trametinib. Discontinue dabrafenib.
 
Report as SAE
 
Consult with cardiologist

Symptomatic Grade 4: resting LVEF $<20\%$
	
Repeat ECHO after 2, 4, 8, 12, and 16 weeks or until resolution
 
Consult with study PI regarding restart of dabrafenib once LVEF recovers

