4.4.4 Management and Dose Modifications for Visual Changes

Episodes of visual changes have been observed in subjects receiving dabrafenib, trametinib or the combination of both therapies. Ocular adverse events are known to be related to trametinib. The causal relationship between a change in vision and the study treatment should be carefully explored and an ophthalmologist should be consulted. However, if the visual changes are clearly unrelated to study treatment (e.g., allergic conjunctivitis), then monitor closely as it may be reasonable to defer ophthalmic examination. Treatment with dabrafenib has been associated with the development of uveitis, including iritis. Monitor patients for visual signs and symptoms (such as, change in vision, photophobia and eye pain) during therapy. For adverse events of uveitis, no dose modifications are required as long as effective local therapies can control ocular inflammation. If uveitis does not respond to local ocular therapy, interrupt dabrafenib and hold until resolution of ocular inflammation. Then restart dabrafenib reduced by one dose level.

Special attention should be given to retinal problems (e.g., retinal pigment epithelium detachments (RPED)) or retinal vein abnormalities (e.g., RVO).

Refer to section 11.1 (Appendices) for grading of visual changes.

If visual changes develop, an eye exam is indicated. The exam will include best corrected visual acuity, tonometry, slit lamp biomicroscopic examination, visual field examination, and dilated indirect funduscopy with special attention to retinal abnormalities. Optical coherence tomography is strongly recommended at scheduled visits, and if retinal abnormalities are suspected. Other types of ancillary testing including color fundus photography and fluorescein angiography are also recommended if clinically indicated.

CTCAE Grade ^a	Management of Visual Changes	Action and Dose Modification for Dabrafenib and Trametinib

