
1st Event Clinical evaluation for infection and hypersensitivity
 
Laboratory work-up^a
 
Hydration as required
 
Administer anti-pyretic treatment if clinically indicated and initiate prophylactic treatment^e if fever associated with rigors, renal failure, dehydration or hypotension
 
2nd Event^b Clinical evaluation for infection and hypersensitivity
 
Laboratory work-up^a
 
Hydration as required
 
Within 3 days of onset of pyrexia:
 
 Optimize anti-pyretic therapy Consider oral corticosteroids (i.e., prednisone 10 mg) for at least 5 days or as clinically indicated 
Subsequent Events: Clinical evaluation for infection and hypersensitivity
 
Laboratory work-up^a
 
Hydration as required^d
 
Within 3 days of onset of pyrexia:
 
 Optimize oral corticosteroid dose as clinically indicated for recalcitrant pyrexia^b If corticosteroids have been tapered and pyrexia recurs, restart steroids If corticosteroids cannot be tapered consult study PI 	
1st Event: Interrupt dabrafenib
 
Continue trametinib (unless fever >104°F or fever complicated by rigors, hypotension, dehydration or renal failure, in which case trametinib should be withheld until fever resolves.) Resume at same or lower dose level.
 
Once pyrexia resolves to baseline, restart dabrafenib at the same dose level
 
If fever was associated with rigors, renal failure, dehydration or hypotension, reduce dabrafenib by one dose level^c
 
2nd Event: Interrupt dabrafenib
 
Continue trametinib (unless fever >104°F or fever complicated by rigors, hypotension, dehydration or renal failure, in which case trametinib should be withheld until fever resolves.) Resume at same or lower dose level.
 
Once pyrexia resolves to baseline, restart dabrafenib at the same dose level
 
If fever was associated with rigors, renal failure, dehydration or hypotension, reduce dabrafenib by one dose level
 
Subsequent Events: Interrupt dabrafenib
 
Continue trametinib (unless fever >104°F or fever complicated by rigors, hypotension, dehydration or renal failure, in which case trametinib should be withheld until fever resolves.) Resume at same or lower dose level.
 
Once pyrexia resolves to baseline, restart dabrafenib reduced by one dose level^c
 
If dabrafenib must be reduced to <75 mg BID, permanently discontinue both study treatments

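### Section 4.4 makes LVEF the only exception to reducing both drugs together, but the pyrexia table lowers dabrafenib while trametinib continues

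*Combined protocol and SAP*

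**What the plan says.** The general rule stands in the opening text of section 4.4: "With the exception of decreased LVEF, both therapies should be reduced simultaneously in response to toxicities". Its scope is any toxicity that the investigator attributes to treatment. It names one exception and has no clause that yields to the later sections.

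Two neighbouring rules in the same section do yield. The cap on reductions begins "Unless otherwise noted in the following sections, a maximum of 2 dose-level reductions for AEs are allowed on this protocol", and the re-escalation rule begins "Unless otherwise noted in the tables below, if an AE resolves to grade 1 or baseline at the reduced dose level".

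Three toxicity-specific sections change one drug only:

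- **LVEF (4.4.3.3), the declared exception.** After recovery from an asymptomatic fall: "Restart with trametinib reduced by one dose level in consultation with study PI" and "Restart dabrafenib at previous dose level".
- **Pyrexia (4.4.8), not declared.** For events after the second, trametinib is continued unless the fever exceeds 104°F or is complicated. For dabrafenib the table says: "Once pyrexia resolves to baseline, restart dabrafenib reduced by one dose level".
- **Uveitis (4.4.4), not declared.** If local therapy fails, dabrafenib is held until the inflammation resolves. "Then restart dabrafenib reduced by one dose level". Trametinib is not mentioned.

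**The concern.** Section 4.4.8 is headed as covering therapy-related pyrexia, so its events fall within the general rule. An investigator who applies section 4.4 lowers both drugs. One who applies the pyrexia table lowers dabrafenib and leaves trametinib where it is. Section 1.5.1 reports pyrexia as the most frequent adverse event with the combination, so the question will probably arise.

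What is at stake is consistent dosing, and the safety margin that goes with it, in a small multicenter trial. Section 4.4 gives trametinib two reduced levels, 1.5 mg and 1 mg, and stops it if a dose below 1 mg would be needed. Take a patient with two pyrexia-driven reductions and no re-escalation. Dabrafenib goes from 150 to 100 to 75 mg twice daily on either reading. Trametinib stays at 2 mg on one reading and reaches 1 mg, its floor, on the other.

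**Working it through.** The plan gives no figure to reproduce. The check compares texts, followed by simple arithmetic on how many patients could be affected.

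**1. Scope.** The section 4.4 sentence governs reduction and says nothing about interruption. Holding dabrafenib alone during a fever therefore does not conflict with it. Only instructions that restart a drug at a lower level count.

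**2. The cases side by side.**

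| Situation | Dabrafenib (specific section) | Trametinib (specific section) | Against section 4.4 |
|---|---|---|---|
| Pyrexia, 1st or 2nd event, uncomplicated, 104°F or less | Same level | Continued | No conflict: nothing is reduced |
| Pyrexia, 1st or 2nd event, uncomplicated, above 104°F | Same level | Withheld, then former or lower level | Soft: agrees only if trametinib also resumes unchanged |
| Pyrexia, 1st or 2nd event, complicated | One level lower | Withheld, then former or lower level | Soft: agrees only if the lower level is chosen |
| Pyrexia, 3rd or later event, uncomplicated, 104°F or less | One level lower | Continued | Firm: both rules cannot be followed |
| Pyrexia, 3rd or later event, complicated or above 104°F | One level lower | Withheld, then former or lower level | Soft, as above |
| Uveitis not controlled locally | One level lower | Not mentioned | Soft: silence can be read together with section 4.4 |

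**3. Does the text settle which rule prevails?** It does not. The general sentence stands between two rules that carry yielding wording, and it lacks that wording. It also names LVEF, which would be unnecessary if specific tables always prevailed, because the LVEF table already states its own single-drug rule.

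**4. How many patients.** Inputs:

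- Planned patients: 20 (section 1.1).
- Any pyrexia on the combination: 51% and 57% (section 1.5.1), 56% (Appendix H), 63% pooled and 76% in Part C (Appendix C). The range is 51–76%.
- Share of affected patients with a single event: about one half (section 1.5.2).

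Ceiling, any pyrexia: 20 × 0.51 = 10.2 and 20 × 0.76 = 15.2, so about 10–15 patients.

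Two or more events: 20 × 0.51 × 0.5 = 5.1 and 20 × 0.76 × 0.5 = 7.6, so roughly 5–8 patients.

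The firm conflict needs at least three events, so fewer patients than this. Patients with a complicated first event add to the soft cases only. Section 4.4.8 says accompanying symptoms such as severe chills or dehydration occurred in a minority of cases, and section 1.5.1 puts grade 3 pyrexia at 4–6%, or 20 × 0.04 = 0.8 to 20 × 0.06 = 1.2 patients. The documents do not report how many patients reached a pyrexia dose reduction.

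For uveitis, Appendix C reports 0 of 55 in Part C and 2 of 202 in the pooled combination group.

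**The case against.** The strongest reply is that the specific table overrides the general sentence. The pyrexia table gives an explicit trametinib instruction at every tier. Its action column, like that of the LVEF table, omits the wording used in most other tables, where the column is headed for both drugs. On this view the missing clause is a drafting gap and most investigators would follow the table. That is a plausible account of how the text arose, and it limits the practical harm. It does not remove the conflict, because the sentence lists a single exception and its neighbours show how an override is written in this section.

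A second reply is that footnote c to the pyrexia table describes dabrafenib reduction after three complicated episodes that supportive care and steroids cannot manage. If that limits the row for subsequent events, the firm case largely turns into a soft one. The row itself carries no such limit, and even then the table would allow trametinib to resume unreduced where section 4.4 would not.

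A reader might infer three stronger points that the documents do not support:

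- **That 10–15 of 20 patients would meet the contradiction.** That figure counts any pyrexia, and uncomplicated first and second fevers of 104°F or less reduce nothing.
- **That interrupting dabrafenib alone also breaks the rule.** Section 4.4 does not require joint interruption.
- **That the ambiguity distorts the kinome comparison.** The protocol already permits varied exposure: dose levels, LVEF reductions, dabrafenib continued after trametinib stops, and biopsies after off-study re-treatment pooled into one data set (section 8.1). Nothing in the documents shows or sizes an added effect.

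**Conclusion.** The inconsistency is real and narrow. It is firm for a third or later uncomplicated fever of 104°F or less, taking the table row as written. It is softer for complicated fever, for fever above 104°F, and for uveitis judged treatment related.

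The number of patients affected cannot be derived from the documents. The ceiling is about 10–15 of 20. Roughly 5–8 would have two or more fevers and fewer would have three or more. These counts assume that pyrexia rates in the cited studies carry over to this trial and that the one-half share with a single event applies across that range.

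The matter concerns dosing consistency and safety for the most common combination toxicity. It does not bear on sample size or power. It deserves correction because the text gives two answers to a dosing question and the repair is small.

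**What to change.** Reconcile the joint-reduction sentence in section 4.4 with sections 4.4.4 and 4.4.8, so that the general rule and the toxicity-specific rules agree on which toxicities are exempt from simultaneous reduction. This can be done by completing the list of exceptions in section 4.4 or by changing the specific sections. In the same edit, state what happens to trametinib in the uveitis text, and whether footnote c limits the row for subsequent pyrexia events. Which rule applies is a clinical decision for the investigator and the supplier, and this review takes no position on it.

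The core change is about one sentence in an amendment, with the IRB approval that section 9.6 requires. No visit, assessment or analysis changes.
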